8.1 Trial design

This is a Phase 1, single-centre, randomised, placebo-controlled FTIH study in healthy subjects. The study is in 2 parts and will investigate single-ascending (Part A) and multiple-ascending (Part B) doses of Neumifil, administered intranasally.

Schematic diagrams of the study design are in section 8.2.

8.1.1 Part A

Enrolment of up to 36 healthy subjects is planned, in up to 5 groups (Groups A1–A5). Groups A1–A3 will consist of 6 subjects each, and Groups A4 and A5 will consist of 9 subjects each.

Subjects will receive a single intranasal dose of Neumifil or placebo. In Groups A1–A3, 4 subjects will receive Neumifil and 2 will receive matching placebo. In Groups A4 and A5, 6 subjects will receive Neumifil and 3 will receive matching placebo. Additional dose levels may be explored in up to 2 optional groups of up to 9 subjects each.

The starting dose for Group A1 is 0.028 mg Neumifil. Subsequent planned doses are given in Table 3.

Table 3 Planned doses in Part A

Group	Planned nominal dose of Neumifil	Number of subjects	Number on placebo
A1	0.028 mg	6	2
A2	0.085 mg	6	2
A3	0.28 mg	6	2
A4	0.885 mg	9	3
A5	2.8 mg	9	3
A6 (optional)	To be decided	9	3
A7 (optional)	To be decided	9	3

Because Neumifil has never been given to humans before, each new ascending dose will be staggered: sentinel subjects will be dosed first, and the remaining subjects will be dosed at least 23 h later. To maintain the blind nature of the study, the 2 sentinel subjects will be randomised to ensure that 1 subject receives active treatment and the other receives placebo. Since 1 subject will receive placebo treatment, the sentinel subjects may be dosed at least 5 min apart. Provided the investigator considers the safety and tolerability in the sentinel subjects to have been acceptable, the remaining subjects will be dosed, at intervals of at least 10 min.

The planned dose levels may be changed, depending on the safety and tolerability results after previous doses, as described in section 8.5. The dose will not be escalated unless the safety and tolerability of the previous dose is acceptable. There will be an appropriate interval between sequential groups, to allow for review of those data. If the dose level selected is no higher than one that has already been shown to cause no safety concerns, sentinel subjects will not be required, and subjects will be dosed at intervals of at least 10 min. The maximum dose will not exceed 2.8 mg.

Subjects will be screened within 35 days before their dose of trial medication.

Subjects will be resident on ward from 1 day before their dose (Day –1) until about 24 h after dosing (Day 2). They will return for a follow-up visit 7–8 days after their dose (Day 8–9).

8.1.2 *Part B*

Enrolment of up to 24 healthy subjects is planned, in up to 3 groups of 8 subjects (Groups B1–B3).

Subjects will receive once-daily intranasal doses of Neumifil or placebo for 7 days. In each group, 6 subjects will receive Neumifil and 2 will receive matching placebo.

[figure not shown]
Part B can start before completion of Part A. The starting dose level (dose and dose regimen) for Group B1 will be decided after review of safety and tolerability data from at least 3 dose levels in Part A, and will be no higher than a dose that has previously been shown to cause no safety concerns in Part A (see section 8.5.3). An additional dose level may be explored in 1 optional group of up to 8 subjects (Group B4). Subsequent doses levels, including maximum duration of dosing, will be determined as described in Part A.

Subjects will be screened within 35 days before their dose of trial medication.

[figure not shown]
Subjects will be resident on ward from 1 day before their dose (Day –1) until about 24 h after their last dose (Day 8). Subjects will attend an outpatient visit at 7–8 days after their last dose (Days 15–16). They will then return for a follow-up visit at 13–15 days after their dose (Days 21–23).

8.2 Study flow chart

[figure not shown]
Figure 3 Study flow chart

Part A

Part B

OP: outpatient visit. Part B can start after review of safety and tolerability data from at least 3 dose levels in Part A. Groups A6, A7 and B4 are optional. Dose selection for Part A and B is described in section 8.5.2 and 8.5.3.

8.3 Definition of the end of the trial

The end of the trial is defined as the final follow-up visit by the last subject. If the trial is terminated prematurely, the trial ends when the sponsor notifies the investigator in writing that the trial has finished, or when the last subject attends the final follow-up visit, whichever is later.

8.4 Stopping criteria

8.4.1 *Trial stopping criteria*

The trial will be stopped if either of the following occurs:

- one or more SAEs considered to be at least possibly related to study treatment; or
- 2 or more severe or clinically significant AEs considered to be at least possibly related to study treatment at any dose level.

Treatment allocations may be unblinded to aid safety review, provided that the unblinding is appropriately documented.

If, after an internal safety review, it is appropriate to restart the trial, a substantial amendment will be submitted to the MHRA and research ethics committee (REC). The trial will not restart until the amendment has been approved by the MHRA and REC.

8.4.2 *Dose escalation stopping criteria*

A dose level will not be repeated, or exceeded, if either of the following apply:

- the results of safety tests give the sponsor or investigator cause for concern
- the investigator or sponsor considers that dose level to be poorly tolerated

The trial will be stopped if any criterion in section 8.4.1 is met.

See section 9.4 for individual subject withdrawal criteria. Dosing will be discontinued in an individual if any criterion in section 9.4 is met.

8.5 Criteria for dose selection

8.5.1 *Review of data by the SRG*

During the study, the dose level (dose and [if applicable] dose regimen) will be increased only if the safety and tolerability of the previous dose level is acceptable.

All dose levels will be selected by the SRG, which will include (as a minimum) the principal investigator (or delegate) and the sponsor's medically qualified

representative (or delegate). Each dose decision will be made and documented in line with HMR SOPs.

Before confirming the dose level for any group, the SRG will review, as a minimum, safety and tolerability data from the previous dose level and (if different) the highest dose level tested to date, as described below. Safety and tolerability data obtained from the previous group(s) will also be reviewed, if applicable. All data used to support dose selection will be quality checked.

Review of safety and tolerability data

The SRG will review (as a minimum) safety and tolerability data, up to 7 days after (final) dosing, from at least 4 evaluable subjects who have received active treatment at the highest dose level tested to date. An evaluable subject is one who completes dosing, has undergone procedures until 7 days after (final) dosing, and has no major protocol deviations. To maintain blinding, data from at least 6 subjects in each group of 6 (Groups A1–A3) or 8 (Groups B1–B3), or from at least 7 subjects in each group of 9 (Groups A4 and A5), must be reviewed to ensure that the dataset includes at least 4 evaluable subjects on active treatment. If fewer subjects than planned are dosed, any subjects required to complete the group may be dosed in parallel with subsequent groups.

The safety data reviewed will include, as a minimum:

- AEs and SAEs, including description, intensity, onset, duration, and relationship to treatment
- vital signs
- 12-lead safety ECG
- laboratory safety tests
- physical examination
- nasal examination
- FEV₁
- tolerability questionnaire

Review of pharmacokinetic data

It is not expected that a review of the PK will form part of the dose escalation decision, as the plasma concentrations are expected to be very low/not detectable. However, if PK data are reviewed, dummy-subject identifiers will be applied to the data by the bioanalytical laboratory, or an unblinded programmer at HMR, so that individual data may be reviewed without unblinding the investigator or any blinded sponsor representatives. If fewer subjects are dosed than planned, to avoid potential unblinding, individual data will not be reviewed – mean, minimum and maximum data will be reviewed, and number of subjects will not be presented. If there are missing PK data at a particular timepoint, the missing data may be replaced by an interpolated value to maintain blinding.

8.5.2 Dose selection for Part A

Planned dose levels in Part A (Table 3) may be changed based on emerging data.

It is expected that the dose level will be increased for each group (Groups A1–A5). The dose will be increased such that it does not exceed 3.5-times the highest dose level that was safe and well tolerated.

Two further dose levels may be explored in the optional groups of subjects (Groups A6 and A7). No dose will exceed 2.8 mg. The trial will be stopped if the criteria in section 8.4.1 are met.

The scheduled dose of Neumifil may be reduced if, for example, the results of safety tests give us cause for concern, or tolerability is poor.

8.5.3 Dose selection for Part B

Part B will not proceed until the SRG has reviewed safety and tolerability data (up to 7 days after dosing) from at least 3 dose levels in Part A, as described in section 8.5.1.

The first total daily dose level (dose and dose regimen [ie once- or twice-daily]) to be tested in Part B will be the same as, or lower than the highest single dose level that has been given in Part A without any safety concerns. For subsequent groups in Part B, the dose level will be escalated only if the safety and tolerability of the previous dose level are acceptable and do not exceed the highest single dose tested in Part A that caused no safety concerns.

The planned duration of dosing (7 days) may be changed based on emerging data but will not exceed 14 days.

8.5.4 Repeating a dose level or selection of a lower dose level (Parts A and B)

In Parts A and B, it is expected that the dose will be increased for each group.

The SRG may decide to test a lower dose level of Neumifil, or to repeat a dose level, provided it does not meet any of the criteria in Section 8.4. Such decisions will be made and documented in line with HMR SOPs. A dose level may be repeated under the following circumstances.

- If it was safe and well tolerated.
- If AEs occur that cause mild or moderate discomfort, but do not in any way threaten the health of the subject, that dose level may be repeated with the aim of exploring further the relationship between dose and AE. If, in the SRG's judgement, it would be unreasonable to expose further subjects to the level of discomfort experienced by the subjects who have already received the dose, a lower dose may be tested. The selected dose will be either a lower dose level that has already been given, or an intermediate level that has not previously been

given; in either case, the aim is to learn more about the relationship between AEs and dose of Neumifil.

9 Trial population

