2.5.2 Part B

Part B is a randomised, double-blind, placebo-controlled, multiple ascending dose study.

Enrolment of up to 24 healthy subjects is planned, in up to 3 groups (Groups B1–B3) of 8 subjects each. Subjects will receive once-daily intranasal doses of Neumifil or placebo for 7 days. In each group, 6 subjects will receive Neumifil and 2 will receive matching placebo.

Part B can start before completion of Part A. The starting dose level (dose and dose regimen) for Group B1 will be decided after review of safety and tolerability data from at least 3 dose levels in Part A and will be no higher than a dose level that has previously been shown to cause no safety concerns in Part A (see section 8.5.3). Subsequent dose levels will be determined as described for Part A. An additional dose level may be explored in 1 optional group (Group B4).

Subjects will be screened within 35 days before their dose of trial medication. Subjects will be resident on ward from 1 day before their dose (Day –1) until about 24 h after their last dose (Day 8). Subjects will attend an outpatient visit at 7–8 days after their last dose (Days 15–16). They will then return for a follow-up visit at 13–15 days after their last dose (Days 21–23).

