The investigator will ask withdrawn subjects to provide written consent to a follow-up examination, to check that they have come to no harm as a result of taking part in the trial. Provided that the subject agrees, they will undergo, at withdrawal from the trial (or as soon as possible afterwards), the standard medical examination and laboratory tests which they would have undergone had they completed it. The investigator will record in the case report form (CRF) the results of the follow-up examination of withdrawn subjects, if they give their consent for that.

9.4.3 *Replacement of withdrawn subjects*

Withdrawn subjects will be replaced at the discretion of the sponsor and investigator. Replacements for withdrawn subjects will receive the treatment(s) intended for the withdrawn subject.

10 *Treatments*

10.1 *Treatments administered*

Part A: subjects will receive a single dose of Neumifil or placebo.

Part B: subjects will receive once-daily doses of Neumifil or placebo for 7 days.

All doses will be administered intranasally using an Aptar liquid delivery system. Each dose will consist of nasal drops/spray administered as a maximum volume of 0.5 mL to each nostril. Subjects must lie supine for 5 min after dosing. Further details will be provided in a separate manual.

Fasting requirements are described in section 11.

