10.6 Selection and timing of dose for each subject

The treatments to be administered are described in sections 8.1 and 10.1. Subjects will be randomly assigned to those treatments, as described in section 10.5 above.

Because Neumifil has never been given to humans before, each new ascending dose in Part A will be staggered as described in section 8.1.

In Part A, all doses will be given in the morning. In Part B, doses will be given once or twice-daily at the same time each day (\pm 15 mins from the time of dosing on Day 1).

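### The upper limit for Part B groups after B1 is stated in two ways that give different maximum doses, with no stated precedence and no single dose unit

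*Combined protocol and SAP*

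**What the plan says.** **Groups after B1, by cross-reference.** The summary (2.5.2) caps B1 at a level that raised no safety concerns in Part A, then adds "Subsequent dose levels will be determined as described for Part A". Section 8.1.2 does the same for B1 and continues "Subsequent doses levels, including maximum duration of dosing, will be determined as described in Part A". In both places the pointer to 8.5.3 is attached to the B1 sentence. The risk section (6.5) also ties only the B1 starting dose to Part A.

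**The Part A rule.** Section 8.5.2 states "The dose will be increased such that it does not exceed 3.5-times the highest dose level that was safe and well tolerated", and adds "No dose will exceed 2.8 mg".

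**Groups after B1, by direct statement.** Section 8.5.3 allows escalation only if safety and tolerability at the previous level are "acceptable and do not exceed the highest single dose tested in Part A that caused no safety concerns".

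**Dose unit.** For B1, 8.5.3 is worded in daily terms: "The first total daily dose level (dose and dose regimen [ie once- or twice-daily]) to be tested in Part B". The sentence on later groups has no daily-total wording.

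**Regimen.** Section 10.1 says "Part B: subjects will receive once-daily doses of Neumifil or placebo for 7 days", and note 13 to the Part B schedule (12.1.2) also says once daily. Section 10.6 says "In Part B, doses will be given once or twice-daily at the same time each day", and section 11 gives fasting rules for a possible evening dose.

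**Sentinels.** Sections 6.5 and 8.1.1 drop sentinel dosing only where the level is no higher than one already shown to raise no safety concerns. Table 4 lists no sentinels for any Part B group.

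**The concern.** The Safety Review Group (SRG) needs one answer to the question of how high the next Part B group may go. A reader of 2.5.2 or 8.1.2 is sent to the Part A method; a reader of 8.5.3 finds a cap at the highest single dose cleared in Part A. The cross-reference in 8.1.2 is also defective on its face. It says that the maximum duration of dosing follows Part A, but Part A is single-dose and has no duration rule. The 14-day maximum appears only in 8.5.3.

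This is a first-in-human repeat-dose escalation, and the protocol plans for Part B to start once three Part A levels have been reviewed. At stake is whether a group without sentinels may receive repeated doses at a level that has not yet been cleared as a single dose. The dose-unit and regimen wording raises a second question: whether the cap on later groups, and the 2.8 mg ceiling, apply to each administration or to the daily total.

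**Working it through.** **Inputs.** Planned Part A doses are 0.028, 0.085, 0.28, 0.885 and 2.8 mg (Table 3). The fold limit is 3.5 and the ceiling 2.8 mg (8.5.2). Part B may start after at least three Part A levels (8.1.2, 8.5.3), so at the earliest after 0.28 mg on the planned doses.

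**Step 1: the plan's own fold limit.** The ratios of consecutive planned doses are 0.085/0.028 = 3.04, 0.28/0.085 = 3.29, 0.885/0.28 = 3.16 and 2.8/0.885 = 3.16. All are within 3.5, so 8.5.2 agrees with Table 3. The difficulty arises only when the rule is carried into Part B.

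**Step 2: maximum level for the group after B1.** Let c be the highest single dose cleared in Part A, and suppose B1 received c once daily without concern. The 8.5.3 maximum is c. The maximum under the Part A rule is the smaller of 3.5 × c and 2.8 mg.

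| c (mg) | 8.5.3 maximum (mg) | 3.5 × c (mg) | Part A rule maximum (mg) | Ratio of maxima |
|---|---|---|---|---|
| 0.28 | 0.28 | 0.98 | 0.98 | 3.50 |
| 0.885 | 0.885 | 3.10 | 2.8 | 3.16 |
| 2.8 | 2.8 | 9.8 | 2.8 | 1.00 |

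The readings diverge while c is below 2.8 mg, that is, while Part B overlaps Part A or if Part A stops early, and they coincide at 2.8 mg. If Part A stopped at 0.28 mg, the Part A rule would allow 0.28, 0.98 and 2.8 mg in B1 to B3 (0.98 × 3.5 = 3.43, held to 2.8). Section 8.5.3 would hold all three groups at or below 0.28 mg.

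**Step 3: dose unit.** This matters only if twice-daily dosing is used. If the cap on later groups is read as a daily total, the maximum per day is c: 0.28, 0.885 or 2.8 mg. If it is read per administration, it is 2 × c: 0.56, 1.77 or 5.6 mg. The same regimen would breach the B1 wording, which is in daily terms. The 2.8 mg ceiling (6.4.2, 6.5, 8.1.1, 8.5.2) does not settle this, because none of those sections says per administration or per day.

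**The case against.** The strongest reply is that the two statements do not exclude each other. Both are upper limits, so an SRG that follows 8.5.3 never breaches the Part A fold limit at the maxima shown above. Section 8.5.3 is the specific section, and the note to the flow chart in 8.2 points to it for Part B. The cross-reference also need not import the 3.5-fold number. In the summary it leads back to 2.5.1, which gives SRG review and no fold limit. In 8.1.2 its extension to duration suggests that a decision process was meant. The sentinel text supports this view: having no sentinels in Part B fits a cap at cleared levels, and 6.5 requires each new ascending dose to be staggered.

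This stands in part. It rules out calling the rules incompatible. It does not remove the ambiguity, because 8.1.1 leads on to section 8.5, where the fold limit is stated, and no section gives precedence.

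A reader might infer more than the documents support on four points:

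- **A 10-fold step in Part B.** Under 8.5.3 alone, 0.28 to 2.8 mg (2.8/0.28 = 10) would be possible once 2.8 mg is cleared. That step ends at a level already cleared as a single dose. Whether a fold limit should apply there is a design preference, not a contradiction.
- **Authorised dosing at 5.6 mg/day.** This needs both twice-daily dosing and a per-administration reading. Section 8.5.1 defines dose level to include regimen, which makes the daily reading the more natural one, although the comparison is still with a single dose.
- **A Part A rule detached from cleared doses.** Section 8.5.2 is tied to the highest safe and well tolerated level, as a multiple of it.
- **Sections 2.5.2 and 8.1.2 excluding twice-daily dosing.** Both describe once-daily dosing but leave the B1 regimen to be decided after review. The unqualified once-daily statements are in 10.1 and note 13.

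**Conclusion.** The point holds as an inconsistency in the written escalation limits. For groups after B1 the text supports two maxima that differ by a factor of 3.5 with 0.28 mg cleared and 3.16 with 0.885 mg cleared, and that agree at 2.8 mg. These figures assume that the planned Part A doses are kept, that B1 is given at the highest cleared single dose without concern, that dosing is once daily, and that the cross-reference brings in the 8.5.2 fold limit. That last reading is open but not compelled.

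The higher reading would place a level not yet cleared in a group without sentinels, contrary to the condition in 6.5 and 8.1.1 for omitting them. The change of dose unit within 8.5.3, the differing regimen statements and the missing time basis for the 2.8 mg ceiling are further ambiguities. The unit question has a numerical effect only with twice-daily dosing. The documents do not show that an uncleared level is intended, and nothing here says which limit is right.

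**What to change.** Reconcile sections 2.5.2, 6.5, 8.1.2, 8.5.2, 8.5.3, 10.1, 10.6, 11 and note 13 to 12.1.2, so that:

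1. one limit governs all Part B groups, and the text says whether the Part A fold limit has any role in Part B;
2. the cross-reference to Part A in 2.5.2 and 8.1.2 is corrected, including its mention of duration;
3. the Part B cap and the 2.8 mg ceiling (also in 6.4.2 and 8.1.1) are given in one stated unit, per administration or per day;
4. the regimen is described the same way throughout;
5. the sentinel provisions agree with the limit chosen.

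Which limit, unit and regimen apply is for the sponsor and investigator to decide. The cost is protocol wording, with no added subjects or procedures. The SRG may have somewhat less freedom in choosing Part B levels.

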9.1 Planned number of subjects

Up to 60 healthy volunteers (up to 36 in Part A and up to 24 in Part B), excluding replacements and optional groups.

9.2 Inclusion criteria

1. Healthy male or female volunteer, aged 18–60 years.
2. BMI (Quetelet index) in the range 18.0–30.9 kg/m².

$$\text{Body Mass Index} = \frac{\text{weight [kg]}}{(\text{height [m]})^2}$$

3. Able to understand the nature of the trial and any hazards of participating in it. Ability to communicate satisfactorily with the investigator and to participate in, and comply with the requirements of, the entire trial.
4. Willingness to give written consent to participate after reading the information and consent form, and after having the opportunity to discuss the trial with the investigator or their delegate.
5. Agree to follow the contraception requirements of the trial as described in section 11.
6. Agree not to donate blood or blood products during the study and for up to 3 months after the administration of the trial medication.
7. Spirometry readings (FEV₁ and FVC) to be $\geq 80\%$ of predicted value at the screening visit, calculated using National Health and Nutrition Examination Survey (NHANES) reference. If a subject's FEV₁ or FVC is outside that range at the screening visit, the test may be repeated once on another day.
8. Registered with a General Practitioner (GP) in the UK (Part A only).
9. Willingness to give written consent to have data entered into The Overvolunteering Prevention System (TOPS).

